7.1. Disposition of Patients/Subjects and Withdrawals

The numbers of patients enrolled, randomized, completing, and withdrawing from treatment and the trial, along with reasons for withdrawal for treatment and trial, respectively, will be tabulated overall and by treatment sequence (Part 1). The number of patients in each analysis set will be reported, as well as the number of patients at each visit. A CONSORT diagram showing patient disposition will be provided.

All disposition information will be listed.

7.2. Protocol Violations and Deviations

Protocol deviations will be listed.

7.3. Demographics and Other Baseline Characteristics

Demographic and baseline characteristics (including age, sex, race, ethnicity, weight, weight z-scores, length/height, and length/height z-scores) will be summarized at screening using descriptive statistics for patients in FAS by treatment sequence. Z-scores (based on the World Health Organization [WHO] growth charts) will be derived using a patient's age and sex. No formal statistical analyses will be performed.

Focal CHI will be described from the general medical history form.

7.4. Exposure and Compliance

Study drug administration will be summarized separately for total dasiglucagon exposure ($\mu\text{g}/\text{kg}$) and length of exposure (days), respectively for Part 1 and Part 2. Moreover, the duration of drug use (days) will be presented. It will be calculated as length of exposure minus number of days without IMP exposure. Additionally, the infusion rate, defined as the average hourly weight-adjusted infusion rate of study drug over the study period analyzed (i.e., $\mu\text{g}/\text{kg}/\text{hr}$ and $\mu\text{g}/\text{hr}$), will be summarized for each Part. For Part 1, the two days of duration will be used for calculation and for Part 2, it will be calculated for each week.

7.5. COVID impact assessment

For all subjects under the study during the COVID pandemic, an assessment of visits missed, visits delayed, visits done remotely, efficacy and/or safety assessments missed will be performed. All protocol deviations related to COVID will be listed.

8. Efficacy Analysis

8.1. Primary Efficacy Analysis

The weighted mean IV GIR in the last 12 hours of each treatment period during Part 1 will be analyzed. The hypothesis:

$$H_{11}: \text{Weighted mean IV GIR}_{\text{dasiglucagon}} = \text{Weighted mean IV GIR}_{\text{placebo}}$$

The weighted mean IV GIR will be based on the last 12 hours of each treatment period, calculated as a weighted mean across the 12 hours, taking the actual time periods between the measurements into account (corresponding to calculating the area under the curve [AUC] and dividing by the length of the time period, i.e., weighted mean IV GIR). The weighted mean IV GIR endpoint is expressed as glucose in $\text{mg}/\text{kg}/\text{min}$, i.e., data reported from different concentrations of the glucose used for infusion will be transformed to this standardized unit prior to analysis. When transitioning each patient between the parts (cross-over from Day 2 to Day 3 and from Day 4 to Day 5), it required from sites approximately 15 minutes of IP disconnection. Because the subject would be disconnected from all IP during this approximately 15-minute

period and to prevent any hypoglycemia, study team from site 101 restarted the subjects on their baseline GIR to provide them with dextrose support while the infusion sets were being changed. Because of this return to baseline GIR prior to the start of the next phase/ start of next IP dosing, it appears in database that for some patients, GIR values are back to baseline before the new IP has been set. As those values are artificial and not linked to any effect of IP, they will have to be removed from statistical analysis. Those GIR values are clearly described in a protocol deviation form and will be clearly identified in blinded data review meeting minutes as non analyzable. They will not be included in any statistical analysis based on IV GIR.

The primary analysis is defined by the estimand based on the treatment policy (de-facto) strategy, where the actual GIR measurement reported irrespective of adherence to treatment (also considering data not under treatment) or use of subsequent therapy is used. The difference in weighted mean IV GIR between placebo and dasiglucagon will be estimated.

The weighted mean IV GIR will be analyzed using a mixed-model regression approach using this programming:

```
PROC MIXED;  
  CLASS PATIENT PERIOD TRT;  
  MODEL OUTCOME= PERIOD TRT / DDFM=KR;  
  RANDOM PATIENT;  
  LSMEANS TRT / PDIFF CL E;  
  RUN;
```

with treatment (TRT) and period as fixed effects and patient as a random effect. Denominator degrees of freedom will be calculated according to Kenward Roger method. The 2-sided 95% confidence interval (CI) for the treatment difference will be calculated from the mixed regression model.

Missing data will be imputed as detailed below:

- if the weighted mean IV GIR is missing for the placebo period, it will be imputed using the baseline IV GIR;
- if the weighted mean IV GIR is missing for the dasiglucagon period, it will be imputed using the placebo-weighted mean IV GIR for that patient.

The primary efficacy analysis will be based on the Full Analysis dataset.

8.1.1. Sensitivity and Supportive Analyses for the Primary Endpoint

As a sensitivity analysis, in case of missing data for primary endpoint, it will also be analyzed:

- using only complete cases cases (i.e., weighted mean IV GIR is non-missing for both placebo and dasiglucagon)- an assessment performed not under treatment will not be considered as missing,
- imputing missing weighted mean IV GIR, for both dasiglucagon and placebo values, using the baseline IV GIR,
- impute missing dasiglucagon values during one period with the placebo value for that patient, imputing missing placebo values with the mean of placebo patients for that period.
- Using tipping point analysis: a 2-way tipping point sensitivity analysis will be performed to investigate the sensitivity for the assumptions on missing data in the

primary analysis for the primary endpoint. Missing GIR values in the dasiglucagon period in part 1 will be imputed with the value for the same patient in the placebo period plus a penalty. Missing GIR values in the placebo period will be imputed using baseline for the same patient plus a penalty. The penalty will be varied independently in the two treatment periods including no penalty in the placebo periods together with increasing penalties in the dasiglucagon periods (penalties will be 0.5, 1, 1.5). For each combination the statistical analysis similar to the primary analysis will be carried out. Scenarios for which statistical significance change will be evaluated with respect to plausibility of the penalties.

- Sensitivity analysis using a placebo multiple-imputation method will be performed. As for each period of cross-over we have only baseline and end of period value, non-monotone imputation is not needed. Monotone missing values will be imputed using the imputation model built from the placebo group in corresponding period, i.e., assuming the missing data in the Dasiglucagon group will have a profile that equals the profile of the Placebo group. The missing data imputation will be implemented using PROC MI in SAS 9.4 using a monotone regression model approach for each period independantly. The baseline GIR will be included as explanatory variable and the value at the end of the period will be included as the outcome variable in the model. The seed to be used in the analysis is 12255070, and 100 imputed datasets will be created. Once the completed data sets are formed, the same analysis model as specified for the primary analysis will be applied to each completed set and the inference drawn using Rubin's combination rules (SAS proc MIANALYZE).

As a sensitivity analysis, as some subjects did not have the same GIR infusion rate at start of each cross-over period, the same analysis as primary analysis will be run adding as covariate period specific baseline (BASEP) and Mean baseline for subject over the two periods (MEANBASE):

```
PROC MIXED;  
CLASS PATIENT PERIOD TRT;  
MODEL OUTCOME= PERIOD TRT BASEP MEANBASE/ DDFM=KR;  
RANDOM PATIENT;  
LSMEANS TRT / PDIFF CL E;  
RUN;
```

As supportive analysis:

- the primary endpoint analysis will be repeated on the PP Set.
- the primary endpoint will be analyzed using a generalized linear model using a log-link and assuming a normal distribution/ With this analysis, exponentiated estimate for treatment effect would give you the mean(GIR) dasi / mean (GIR) placebo/. Following program will be used:

```
PROC GENMOD;  
CLASS PERIOD TRT;  
MODEL OUTCOME= PERIOD TRT / LINK=LOG DIST=NORMAL ;  
REPEATED SUBJECT=PATIENT/ TYPE=CS;  
ESTIMATE "DASIGLUCAGON versus PLACEBO" TRT 1 -1 / EXP;  
RUN;
```

These sensitivity and supportive analyses will not be included in the fixed-sequence hierarchical testing strategy.

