2.1. Study Objectives

2.1.1. Primary Objective

The primary objective is to evaluate the efficacy of dasiglucagon in reducing glucose requirements in children with persistent congenital hyperinsulinism (CHI) requiring continuous IV glucose administration to prevent/manage hypoglycemia.

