3.4. Treatments Administered

During the part 1, cross-over period, patient will receive Dasiglucagon and Placebo. During Part 2, patients will receive only Dasiglucagon.

Part 1 dispensing unit configuration: 3 vials containing dasiglucagon, 4 mg/mL in a 3 mL vial containing 1 mL of drug product or placebo in a 3 mL vial containing 1 mL of drug product. Dasiglucagon and matching placebo will be provided in the form of solution for injection for subcutaneous administration through an infusion pump.

As long as the patient is receiving IV glucose, the PG will be measured and reviewed hourly using a hand-held PG meter. The IV GIR will be titrated to achieve glycemia of at least 70 mg/dL (3.9 mmol/L) (a minimum GIR will be established as the rate up-titrated after the patient drops at least once below 70 mg/dL [3.9 mmol/L]). When the patient is no longer on IV GIR, the PG will be checked according to local practice, but at least 3 times daily. The PG will be measured using the same trial-supplied hand-held PG meter during the entire trial.

Additionally, blinded CGM will be started 24 hours prior to randomization (using the Dexcom G4 system) and continued until the end of Part 2.

Dosing of dasiglucagon will approximate continuous infusion by delivering small doses at frequent intervals via the infusion pump. The adjustment of trial drug dosing is closely linked to the PG level achieved, which in turn will govern the IV GIR. In Part 1 the algorithm in Table 1 should be used.

The pump administers 0.000025 mL/dose ~ 0.1 µg/dose (4 mg/mL formulation):

- 10 µg/hr ~ 0.5 µg every 3 min
- 20 µg/hr ~ 1 µg every 3 min
- 30 µg/hr ~ 1.5 µg every 3 min
- 40 µg/hr ~ 2µg every 3 min
- 50 µg/hr ~ 2.5µg every 3 min
- 60 µg/hr ~ 3µg every 3 min
- 70 µg/hr ~ 3.5µg every 3 min

Table 1 Algorithm to maintain plasma glucose

Plasma Glucose (mg/dL)	Plasma Glucose (mmol/L)	Action
<50	<2.8	Give 200 mg/kg of dextrose as a bolus and increase IV GIR by 2 mg/kg/min
50-59	2.8-3.3	Increase IV GIR by 2 mg/kg/min
60-69	3.3-3.9	Increase IV GIR by 1 mg/kg/min
70-80	3.9-4.4	No change
81-90	4.4-5.0	Reduce IV GIR by 0.5 mg/kg/min
91-100	5.0-5.5	Reduce IV GIR by 1 mg/kg/min
101-120	5.5-6.7	Reduce IV GIR by 1.5 mg/kg/min
>120	>6.7	Reduce IV GIR by 2 mg/kg/min

Abbreviations: GIR = glucose infusion rate; IV = intravenous

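### The tipping-point analysis adds its penalty to missing placebo GIR values, which moves the estimate toward dasiglucagon instead of testing against it.

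*SAP*

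**What the plan says.** The objective is to "evaluate the efficacy of dasiglucagon in reducing glucose requirements in children" (SAP 2.1.1), and SAP 8.1 sets the contrast: "The difference in weighted mean IV GIR between placebo and dasiglucagon will be estimated". A lower GIR on dasiglucagon is the benefit.

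In the primary analysis (SAP 8.1) a missing placebo value is replaced by the infant's baseline GIR. For a missing dasiglucagon value, "it will be imputed using the placebo-weighted mean IV GIR for that patient".

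SAP 8.1.1 adds a two-way tipping-point analysis built on these rules. A missing dasiglucagon value becomes the infant's placebo value plus a penalty. For placebo: "Missing GIR values in the placebo period will be imputed using baseline for the same patient plus a penalty". On the grid: "The penalty will be varied independently in the two treatment periods", including no placebo penalty combined with "increasing penalties in the dasiglucagon periods (penalties will be 0.5, 1, 1.5"). No negative value and no separate placebo list is given. Scenarios in which significance changes are then to be judged for plausibility.

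**The concern.** A tipping-point analysis should worsen the missing-data assumption against the drug until the conclusion changes, so that readers can judge whether that point is plausible. Here the two penalties pull in opposite directions. Adding to dasiglucagon shrinks placebo minus dasiglucagon; adding to placebo widens it.

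Three things follow:

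- If only placebo values are missing, every listed scenario is neutral or favours the drug.
- If placebo and dasiglucagon values are missing in different infants, the placebo penalty offsets the dasiglucagon penalty.
- If both periods are missing in one infant, the dasiglucagon value is built on the imputed placebo value and the placebo penalty cancels.

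The untested direction can occur. SAP 3.4 says "In Part 1 the algorithm in Table 1 should be used", and that table lowers the infusion at every plasma glucose above 80 mg/dL, beginning with "Reduce IV GIR by 0.5 mg/kg/min". A placebo mean can therefore finish below the end-of-run-in baseline. The documents do not say how often.

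**Working it through.** **Inputs.** Mean difference 7.5 and SD of differences 7.36 mg/kg/min, n = 12, one-sample t-test (SAP 3.2); two-sided alpha 0.05 (SAP 4.1). Assumed, because the SAP does not say: 1 to 3 missing values, and the same 0.5/1/1.5 list for placebo, in mg/kg/min.

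**The plan's own figure.** Noncentrality = 7.5/7.36 × √12 = 3.53; critical t on 11 df = 2.201; power = 89.4%. The stated 89% reproduces.

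**Sign.** With balanced sequences each infant's difference has weight 1/12. A penalty of 1.5 on one missing placebo value moves the estimated reduction by 1.5/12 = +0.125, toward the drug. A mixed model with a random patient effect, fitted to an illustrative dataset, agrees: dasiglucagon minus placebo goes from -8.72 to -8.84 at +1.5 and to -8.59 at -1.5.

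**Placebo axis.** Let 12 - k observed differences have mean m and SD 7.36, and let k imputed differences equal m + δ, where δ is the shift applied to the placebo value. Then:

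- mean = m + kδ/12
- sum of squares = (11 - k) × 7.36² + [k(12 - k)/12] × δ²
- SD = √(sum of squares/11), and t = mean/(SD/√12) on 11 df

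Example, k = 1, δ = +1.5: mean 7.625, SD 7.03, t = 3.76, p = 0.0032.

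| Missing placebo values | p at 0 | p at +1.5 | p at -1.5 | Tipping shift, m = 7.5 | Tipping shift, m = 5.0 (assumed) |
|---|---|---|---|---|---|
| 1 | 0.0035 | 0.0032 | 0.0039 | -20.3 | -5.3 |
| 2 | 0.0025 | 0.0020 | 0.0032 | -13.1 | -4.0 |
| 3 | 0.0016 | 0.0012 | 0.0024 | -10.2 | -3.5 |

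The p-value columns are for m = 7.5. Every tipping value is negative. From the 10 mg/kg/min entry floor (Protocol 9.2.3), none of the m = 7.5 values can be reached without a negative GIR. From 18.5, the pre-glucagon median of the cohort cited in SAP 3.2, the second and third can. The m = 5.0 values are reachable from either.

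**One placebo and one dasiglucagon value missing, in different infants (m = 7.5).** Imputed differences are 7.5 + placebo shift, and 0 - dasiglucagon penalty.

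| Placebo shift, dasiglucagon penalty | Estimate | p |
|---|---|---|
| 0, 0 | 6.875 | 0.0059 |
| 0, +1.5 | 6.750 | 0.0074 |
| +1.5, +1.5 | 6.875 | 0.0068 |
| -1.5, +1.5 | 6.625 | 0.0083 |

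With both penalties at 1.5 the estimate returns to its unpenalised value.

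**Borderline trials.** Simulation of 200,000 crossovers (6 + 6 infants, design values, treatment-plus-period model on 10 df; baseline assumed equal to placebo on average). Among results with p between 0.01 and 0.05 (24% of trials), the share losing significance was:

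| Placebo shift | 1 missing | 2 missing | 3 missing |
|---|---|---|---|
| +1.5 (as written) | 0.11% | 0.03% | 0.00% |
| -1.5 | 4.6% | 9.3% | 14.5% |
| -5 | 19.2% | 42.1% | 63.8% |

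The small losses at +1.5 arise because a shift on an outlying infant can inflate the SD.

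**Dasiglucagon axis.** The imputed difference is minus the penalty, so this axis starts by giving up the infant's whole effect. At the design values it tips at 12.8, 5.6 and 2.7 for 1, 2 and 3 missing values. The listed maximum of 1.5 would find no tipping point there.

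**The case against.** The defence has real points. Complete-case analysis, imputation by the placebo-period mean and placebo-based multiple imputation (SAP 8.1.1) are not tied to baseline. If the algorithm drives placebo GIR below baseline, the observed placebo values will show it and the latter two carry it into the imputation. That stands as partial cover, but each is a single assumption and none is varied until the result tips.

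The grid includes the row with no placebo penalty and rising dasiglucagon penalties, which is adverse and is to be reported with the rest. That stands too, but it helps only when dasiglucagon values are missing. One could also read a penalty in either period as meaning that an infant with missing data needs more glucose. That is coherent clinically, yet it does not make the placebo axis a stress test of a positive result.

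Reversing the sign within 1.5 changes little: at an assumed mean of 5.0, a shift of -1.5 gives p = 0.035, 0.032 and 0.028 for 1, 2 and 3 missing values, all still significant. That is correct, and is why the range should be extended as well. The larger percentages above combine a -5 shift with an already borderline result.

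Finally, the analysis may never run. It is conditional on missing primary data, off-treatment GIR counts as observed, Protocol 20.4.3 expects low drop-out, and the analysis is outside the hierarchy. This limits the consequence but does not correct the rule.

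**Conclusion.** The concern holds. The placebo axis has the wrong sign for its purpose, and this depends only on the direction of the contrast, not on any assumed number. As written, the analysis gives no tipping value for missing placebo data, and cells with both penalties look somewhat more robust than they should. The fault is confined to the placebo axis.

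The practical size is small at the design values and with few missing observations. It becomes material for a borderline primary result with one or more placebo values missing, which is when a tipping-point analysis would be consulted. The sizes rest on 1 to 3 missing values, an assumed placebo grid and, for the reachable tipping values, an assumed observed mean of 5.0. The correction should be made; it does not put the primary analysis itself in doubt.

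**What to change.** Amend SAP 8.1.1 before unblinding, for example:

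> Missing placebo GIR will be imputed as the patient's baseline minus delta_P, not below 0. Missing dasiglucagon GIR will be imputed as the patient's placebo value plus delta_D. Both are in mg/kg/min and are varied independently from 0 in steps of 0.5. If the primary result is significant, each is extended until p ≥ 0.05 or, for delta_P, until the imputed GIR reaches 0. The tipping values, or that none exists, will be reported and judged for plausibility.

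The sign reversal is the essential change; the wider range is a cheap addition. The text should also state how far the joint grid runs, what is done if the primary result is not significant, and that the placebo shift cancels when both periods of one infant are missing.

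The cost is a few sentences and a changed loop. At the design values that is at most about 26 × 37 model fits (12.8/0.5 rounded up, and 18.5/0.5). No new data are needed. No protocol amendment is needed either: SAP section 10 lists the tipping analysis as an addition, and Protocol 13.4.3.1 does not include it. The only downside is that a reported tipping value may look less favourable.

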3.1. Overall Design

3.2. Sample Size and Power

A total of 12 patients is planned to be randomized and exposed to trial drug in this crossover trial on the basis of the following considerations. The GIR results from 40 infants treated with IV glucagon for 24 hours published in the JIMD Research Report “The Effect of Continuous Intravenous Glucagon on Glucose Requirements in Infants with Congenital Hyperinsulinism”³ (Hawkes et al 2019).

“Overall there was a statistically significant reduction in the median (IQR) GIR during the 24h following initiation of continuous glucagon infusion compared to 24 h before initiation (18.5 (12.9, 22.8) to 11 (6.6, 17.5) mg/kg/min.”

This trial is powered to detect an effect in GIR for dasiglucagon after 48 hours compared to placebo of at least this effect size. Based on the longer infusion and titration of dasiglucagon in this trial, this is considered a conservative approach, allowing for some uncertainty when translating the published data into a clinical trial setting. Using unpublished individual patient data from the above-referenced study, the difference in GIR between the 2 treatment groups is assumed to follow a normal distribution. Assuming the true mean difference is 7.5 mg/kg/min with a standard deviation of differences of 7.36, the trial will have 89% power using a one-sample t-test with 12 patients randomized to receive either placebo first and then dasiglucagon or vice versa.

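### The tipping-point penalties stop at 1.5 with no rule to go further, so under the planning assumptions the analysis would usually end without locating a tipping point

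*SAP*

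**What the plan says.** SAP 8.1.1 lists the tipping-point analysis among the sensitivity analyses to be run "in case of missing data for primary endpoint". It has two arms:

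- A missing dasiglucagon value is "imputed with the value for the same patient in the placebo period plus a penalty".
- For the other treatment, "Missing GIR values in the placebo period will be imputed using baseline for the same patient plus a penalty".

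The two penalties vary independently, "including no penalty in the placebo periods together with increasing penalties in the dasiglucagon periods". The values are fixed: "penalties will be 0.5, 1, 1.5". The primary model is refitted for each combination, and the only interpretive step is this: "Scenarios for which statistical significance change will be evaluated with respect to plausibility of the penalties".

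SAP 8.1 already sets a missing dasiglucagon value equal to the patient's placebo value and a missing placebo value equal to baseline. A penalty of zero in both arms is therefore the primary analysis. SAP 10 records the tipping-point analysis as an addition to the protocol's plan.

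**The concern.** A tipping-point analysis worsens the imputed values until the conclusion changes, and then asks whether values that bad are believable. The output of interest is the tipping value. This grid ends at a fixed, unexplained point. If no scenario on it changes significance, the SAP leaves nothing to evaluate, and the report can say only that the result held up to 1.5. A reader could not tell a result that would fail at 2 from one that would hold to 13.

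The placebo arm has a separate gap. Lower GIR on dasiglucagon is the benefit, so adding a positive penalty to an imputed placebo value widens the difference in the drug's favour. Where placebo is missing and dasiglucagon is observed, no listed penalty moves the estimate against the drug.

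**Working it through.** **Inputs.** SAP 3.2 gives 12 patients and the planning values: "Assuming the true mean difference is 7.5 mg/kg/min with a standard deviation of differences of 7.36". The test is two-sided at 0.05 (SAP 4.1). The number missing is not in the documents (Protocol v14.0, section 20.4.3, says only that drop-out should be low), so m = 1, 2 and 3 missing dasiglucagon values are assumed.

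**The plan's own figure.** For a one-sample t-test on 11 df, the noncentrality is 7.5/7.36 × √12 = 3.53 and the critical value is 2.201. Power is 89.4%, which reproduces the stated 89%.

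**Set-up.** Work with placebo-minus-dasiglucagon differences. The 12 − m observed differences have mean 7.5 and SD 7.36. Each imputed difference equals −d, where d is the penalty. Then:

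- mean = [(12 − m) × 7.5 − m × d] / 12
- SS = (11 − m) × 7.36² + [(12 − m) × m / 12] × (7.5 + d)²
- t = mean / √(SS/11/12), on 11 df

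**One missing, in full.**

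- d = 0: mean = 82.5/12 = 6.875; SS = 541.70 + 0.9167 × 56.25 = 593.26; SE = 2.120; t = 3.243; p = 0.0078.
- d = 1.5: mean = 81/12 = 6.75; SS = 541.70 + 0.9167 × 81 = 615.95; SE = 2.160; t = 3.125; p = 0.0097.
- d = 12.8: mean = 69.7/12 = 5.808; SS = 541.70 + 0.9167 × 412.09 = 919.45; SE = 2.639; t = 2.201, the critical value.

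**All cases.**

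| Missing | Mean at 0 → 1.5 | p at 0 → 1.5 | Tip, 11 df | Tip, 10 df |
|---|---|---|---|---|
| 1 | 6.875 → 6.75 | 0.0078 → 0.0097 | 12.8 | 12.4 |
| 2 | 6.25 → 6.00 | 0.0126 → 0.0185 | 5.6 | 5.4 |
| 3 | 5.625 → 5.25 | 0.0195 → 0.0333 | 2.7 | 2.6 |

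The 10 df column allows for the period term by using the 10 df critical value with the same t statistic. If SS is also divided by 10 instead of 11, the tips are 11.1, 4.5 and 2.0, still beyond the grid. The full penalty moves the mean difference by only 1.5 × m/12 = 0.125, 0.25 or 0.375.

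**When the grid does reach a tip.** Keep the SD at 7.36 and lower the observed mean until p at d = 1.5 is exactly 0.05. The p-value at d = 0 is then about 0.043, 0.036 and 0.030 for m = 1, 2 and 3 (11 df). So the grid finds a tip only when the primary p-value is already above roughly 0.03 to 0.04. Two examples: with an observed mean of 5.8 and two missing the tip is at 1.5; with 6.5 and three missing it is at 1.3.

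**How often.** In 200,000 simulated trials per scenario (six patients per sequence, period-adjusted test on 10 df), the share of results significant at d = 0 that lose significance by d = 1.5 was:

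| True effect | 1 missing | 2 missing | 3 missing |
|---|---|---|---|
| 7.5 | 2.5% | 7.5% | 16.0% |
| 5 | 6.8% | 17.1% | 30.5% |

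**The case against.** Four points on the other side deserve weight.

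1. **The start is already severe.** The imputed patient has zero effect before any penalty; at 1.5 that patient is 7.5 + 1.5 = 9.0 mg/kg/min worse than planned. Comparing 1.5 with 7.5 alone (a fifth) understates the stress. This stands. But zero effect is the primary imputation itself, so the tipping-point analysis adds no more than 1.5 to what has already been assumed.

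2. **Very large tips are not plausible.** With one value missing, a tip of 12.8 means that an infant needs that much more glucose on drug than on placebo. Added, for illustration, to the cited cohort's pre-glucagon median of 18.5, this gives 31.3, against an upper quartile of 22.8. Failing to tip before such values is real evidence of robustness. That too stands, and it is why the search needs a plausibility bound. It does not cover three missing values, where the tip is near 2.6 and goes unexamined.

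3. **Missing data are examined elsewhere.** SAP 8.1.1 also plans complete-case, baseline, placebo-mean and placebo multiple-imputation analyses. A reader might infer that robustness to missing data goes untested; the documents do not support that. Each of these, however, makes one fixed assumption, and none searches for the point of failure.

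4. **The reach is small.** The analysis runs only if data are missing, the treatment-policy estimand keeps off-treatment measurements, and these analyses sit outside the testing hierarchy.

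A reader might also set 1.5 against the hourly titration table in SAP 3.4, which includes "increase IV GIR by 2 mg/kg/min". That comparison does not help: the table also has steps of 0.5, 1 and 1.5, and one hourly adjustment is not a shift in a 12-hour weighted mean.

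**Conclusion.** The concern holds as a limited one. The grid is fixed without justification or an extension rule. If 1, 2 or 3 of 12 dasiglucagon values are missing and the planned effect is seen, it stops short of tips at about 12 to 13, 5.5 and 2.6 mg/kg/min. At a true effect of 7.5, roughly 84% to 97.5% of significant trials would finish without a tipping value. It is tempting to conclude that the grid can never tip, or that it guarantees a robust verdict. The simulation shows otherwise: tips inside the grid do occur, mostly when the primary result is close to p = 0.05. Nor does the SAP say that it will claim robustness.

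The one-sided placebo penalties are a second, separate weakness.

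The figures rest on the assumed number missing, penalties in mg/kg/min, observed values equal to the planning values, and a t-test in place of the mixed model. The primary analysis is not affected.

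**What to change.** Replace the fixed list in SAP 8.1.1 with a search rule:

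- State the unit, and raise the dasiglucagon penalty in 0.5 mg/kg/min steps until p exceeds 0.05 or the imputed GIR exceeds the largest GIR observed in the trial.
- Report the tipping value, or that none was reached within that bound, next to the observed range of placebo-minus-dasiglucagon differences.
- For missing placebo values, also run negative penalties, so that this arm can move the estimate against dasiglucagon.

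The cost is two or three sentences in the SAP and a longer loop in the same program. Trial conduct, data collection, the primary analysis and the testing hierarchy are unchanged.
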